1.0 Background

The prevalence of nonalcoholic fatty liver disease (NAFLD) is not well defined in U.S. adults with HIV infection in the current era. Chronic liver disease is a major cause of morbidity and mortality among individuals with HIV infection (1, 2). With the availability of effective therapies for hepatitis B and C, NAFLD is predicted to become the leading cause of liver disease in the aging HIV population (3). In the non-HIV population, NAFLD is associated with a) increased overall and liver-related mortality (4); b) increased risk for cardiovascular disease and type 2 diabetes (5-9); and c) increased risk for liver cancer even in absence of cirrhosis or significant fibrosis (10-14). In HIV infected patients, the prevalence of NAFLD has not been well established. Reported prevalence has varied by study inclusion criteria and modality of NAFLD diagnosis, ranging from 15-54% when assessed by imaging modalities (15-17) and up to 73% in studies including liver biopsy (18). These studies suffered several limitations, including the inclusion of only a small number of HIV infected individuals (18, 19), inclusion of patients with concurrent hepatitis C infection (20-23) or limiting the HIV population assessed to only military personnel and their dependents or to men alone (15, 16).

The risk factors for NAFLD and NASH in HIV infected individuals have not been examined in depth. First, traditional risk factors for NAFLD in the general population may not apply to NAFLD in those with HIV infection. While most studies suggest an influence of insulin resistance, obesity and dyslipidemia on the risk of NAFLD in HIV infected individuals, this may not apply to male HIV patients who tend to be more physically fit, have similar or lower BMI and lower incidence of fatty liver compared to controls (16, 35, 40). Thus, it is essential to comprehensively evaluate NAFLD and NASH in both women and men with HIV infection and stratify by the metabolic syndrome and BMI to accurately determine prevalence in different risk groups.

The impact of novel antiretroviral agents on risk for NAFLD and NASH has not been comprehensively evaluated. Some antiretroviral agents, particularly nucleoside or nucleotide reverse transcriptase inhibitors (NRTI) and protease inhibitors (PI), impair autophagy and mitochondrial function leading to lipodystrophy, insulin resistance, steatosis and steatohepatitis. (38, 41-46). There are, however, conflicting data from clinical studies on the contribution of ART to this risk and the impact of new antiretroviral agents with better metabolic profiles, such as integrase inhibitors, on the risk of NAFLD (15, 18, 20, 35, 47, 48).

Safe and effective therapies for NASH in HIV infected individuals are absent. Over the last decade, there have been several large randomized clinical trials (with more than a hundred ongoing Phase 2 and Phase 3 currently registered on Clinicaltrials.gov) to treat NASH in the general population, but the majority of them systematically excluded HIV infected individuals (74). Weight loss, exercise and therapy with vitamin E or pioglitazone have shown efficacy in improving NASH and are recommended for HIV uninfected patients with NASH (75). However, whether these measures will be effective in HIV infected individuals with NASH is unknown. A pilot study showed that in patients with HIV and

Vitamin E for NASH Treatment in HIV Infected Individuals

abdominal adiposity on stable ART, Tesamorelin, a growth hormone-releasing hormone analog, resulted in reduction of visceral and liver fat (76). Whether this expensive agent will be useful to treat NASH in HIV infected patients has not been established. Vitamin E is an attractive and inexpensive therapy for NASH in HIV infected individuals. Oxidative stress contributes to the progression of NASH (77-82). Based on its known function as an antioxidant (83), we and others have studied vitamin E used alone or with other compounds in multiple trials to treat NASH or NAFLD in the non-HIV population (84-93). Variable dosages ranging from 100-1200 IU/daily have been used with reported beneficial effects on liver enzymes, steatosis, inflammation, ballooning, and hepatic fibrosis. Duration of vitamin E monotherapy in these trials ranged from 4 to 96 weeks (92, 94). Vitamin E can decrease ALT levels in as early as 4 weeks (92) and improve histology in 6 months (87, 88). In the largest randomized trial, PIVENS (90), vitamin E was given at a dose of 800 IU/daily for 96 weeks and compared to pioglitazone or placebo. Vitamin E and pioglitazone improved ALT, steatosis, lobular inflammation, and ballooning and resulted in resolution of NASH in many patients. Vitamin E, however, was not associated with weight gain as was pioglitazone. Of note, low vitamin E levels were found in 7% of HIV infected men in one study (95), and certain ART regimens have been associated with lower vitamin E levels (96). Earlier small studies suggested potential reduction in oxidative stress and HIV viral loads and increased viability of circulating lymphocytes with vitamin E supplementation (97, 98). Thus, there is a strong rationale to investigate vitamin E as a therapy for NASH in the HIV infected individuals.

Vitamin E for NASH in the non-HIV infected population: The efficacy of vitamin E for NASH was best established with the PIVENS study, one of the largest randomized trials in NASH to date (90). Indiana University was a major participating center in this study. Vitamin E was given at dose of 800 IU/daily for 96 weeks and compared to pioglitazone or placebo. Vitamin E and pioglitazone improved ALT, steatosis, lobular inflammation, and ballooning and resulted in resolution of NASH in a significant number of patients (Figure.4). Vitamin E has not been tested previously as a therapy for NASH in HIV infected individuals.

2.0 Rationale and Specific Aims

The aim of this study is to conduct a proof-of-concept clinical trial to evaluate the efficacy of vitamin E for treatment of NASH in HIV infected individuals.

This project is a proof-of-concept, randomized controlled trial to test the hypothesis that vitamin E improves hepatic steatosis and markers of hepatic necroinflammation in HIV infected individuals with biopsy-proven NASH. In this placebo-controlled, double-blind, randomized pilot clinical trial we will randomize 56 eligible participants at two different sites to receive 800 IU/daily of vitamin E or matching placebo for 6 months. The primary endpoint is the change in hepatic fat content from baseline to end of treatment in the two groups. Subjects will undergo MR imaging to measure hepatic fat content using MR-PDFF at baseline and at the end of treatment. In the randomization visit, all participants will receive standard recommendations about lifestyle modifications including healthy

Vitamin E for NASH Treatment in HIV Infected Individuals

dieting, exercise, and weight loss, and use of alcohol and dietary and herbal supplements.

Vitamin E is a well-established therapy for NASH in the non-HIV population (see section B.5 in Significance). While variable dosages ranging from 100-1200 IU/daily have been used with reported beneficial effects on liver enzymes and histology, including steatosis, the dose chosen in this trial is the same used in PIVENS, the largest randomized clinical trial establishing the efficacy of vitamin E (90) and is the dose recommended by the multi-society guidelines for treatment of NASH in the non-HIV population (75). As vitamin E effects on ALT could be seen in as early as 4 weeks (92) and on histology in 6 months (87, 88), we believe the 6 month duration of the proposed proof-of-principle study is rational. Further, there is emerging data to suggest low vitamin E level may be seen in a small subset (7%) of HIV infected men (95) and in association with use of certain ART (96). Benefits reported with vitamin E use in the HIV infected patient in earlier small studies include reduction in oxidative stress and HIV viral load and increased viability of circulating lymphocytes with (97, 98). Finally, vitamin E is relatively inexpensive and has no interactions with any ART drugs. Thus, there is a strong rationale to investigate vitamin E as a therapy for NASH in the HIV infected individuals.

A total of 56 subjects at two sites will be enrolled in this trial, with approximately 28 individuals included at IU and 28 at Massachusetts General Hospital. Subjects will be randomly assigned to either Group A or Group B.

Group A: Vitamin E (RRR alpha-tocopherol) 800 IU/daily for 24 weeks.
Group B: Matching placebo for 24 weeks.

3.0 Inclusion/Exclusion Criteria

Inclusion criteria:

1. males and females ≥21 years with biopsy-proven NASH within 6 months prior to enrollment
2. histological diagnosis of NASH will be confirmed by an experienced liver pathologist before study entry
3. HIV infection
4. stable dose of anti-diabetic agents and ART in the 3 months preceding enrollment and expected by the physician treating diabetes and HIV to remain on stable medications during the study
5. stable dose of tesamorelin in the 6 months preceding enrollment
6. willingness to participate in the study
7. ability to understand and give informed consent for participation
8. willing to stop use of Vitamin E and/or multivitamins containing Vitamin E at time of enrollment and for the duration of participation in the study

Exclusion Criteria:

1. Presence of other chronic liver diseases (hepatitis B or C, autoimmune hepatitis, cholestatic liver disease, Wilson disease, hemochromatosis, etc.)
2. average alcohol consumption >3 drinks/day for men or >2 drinks/day for women in the 6 months prior to enrollment.

Vitamin E for NASH Treatment in HIV Infected Individuals

3. Alcohol Use Disorder Identification Test (AUDIT) score 8 or more
4. ongoing use of medications known to cause hepatic steatosis (e.g., corticosteroids, amiodarone, methotrexate, tetracycline, tamoxifen, estrogens at doses greater than those used for birth control, anabolic steroids, or valproic acid)
5. prior bariatric surgery
6. severe co-morbidities (e.g., advanced cardiac, renal, pulmonary, or psychiatric illness, as defined as at least one suicide attempt in the past 12 months)
7. allergy to vitamin E
8. use of drugs with potential effect on NASH such as ursodeoxycholic acid, S-adenosylmethionine (SAM-e), betaine, pentoxifylline, or milk thistle in the three months prior to enrollment.
9. changing doses of statins (simvastatin, pravastatin, atorvastatin, fluvastatin, lovastatin, rosuvastatin) or fibrates (clofibrate, fenofibrate) in the three months prior enrollment.
10. illicit substance abuse within the past twelve months, except for marijuana
11. breast feeding, pregnancy, inability or unwillingness to practice contraception for the duration of the study
12. contraindications for the MRI procedure (e.g., prostheses, severe claustrophobia).
13. poorly controlled diabetes with A1C >9 within in the last six months
14. use of total parenteral nutrition in the 6 months preceding liver biopsy or enrollment
15. has decompensated cirrhosis, as defined by the presence of ascites, variceal bleeding, and/or encephalopathy

4.0 Enrollment/Randomization

Participants found to have NASH will be reviewed for their eligibility to participate in this protocol. Eligible subjects will be contacted about this study and interested individuals will enter the screening phase of the protocol.

Screening period: Eligible subjects will be screened within six weeks prior to randomization. The following procedures will take place at the screening visit:

1. Complete explanation of the study, including all study visits and procedures and administration of the informed consent statement and HIPAA Authorization form.
2. An AUDIT questionnaire to determine alcohol consumption will be administered. Eligible subjects will be required to obtain a score of less than 8 on the questionnaire.
3. Current social and medical history will be thoroughly reviewed.
4. Inclusion and exclusion criteria will be verified during this visit.
5. Female subjects of child-bearing potential will have a urine pregnancy test and the pregnancy test must be negative to participate in the study
6. Information to be collected includes:
 - a. age
 - b. sex
 - c. race
 - d. ethnicity
 - e. past medical and medicinal history
 - f. BMI

Vitamin E for NASH Treatment in HIV Infected Individuals

- g. waist and hip circumference measurements
- h. vital signs, including blood pressure, respiratory rate, heart rate, temperature
- i. historical laboratory values from medical records, including:
 - i. serum electrolytes
 - ii. liver profile
 - iii. renal parameters
 - iv. insulin
 - v. glucose
 - vi. A1C level
 - vii. lipid profile
 - viii. HIV viral load
 - ix. CD4 count

Randomization-baseline evaluation visit

1. Subjects will return no more than six weeks after the completion of the screening visit for a baseline evaluation and randomization into the study. All eligible subjects who have provided informed consent and who have met all the inclusion criteria and none of the exclusion criteria will have multiple evaluations performed prior to randomization. This baseline evaluation will be conducted in a single study visit. Subjects will be asked to fast overnight and will undergo the following activities: review of medical history
2. detailed review of medications history
3. administration of the AUDIT questionnaire to capture alcohol use with a score less than 8 in order to participate in the study
4. collection of vital signs
 - a. height
 - b. weight
 - c. blood pressure
 - d. heart rate
 - e. respiratory rate
 - f. temperature
5. focused physical examination
6. measurement of waist and hip circumference
7. approximately 50mL of blood during a fasting state will be collected for the following tests:
 - a. liver profile
 - b. complete blood count
 - c. lipid
 - d. insulin
 - e. glucose
 - f. INR
 - g. MDA
 - h. K-18
 - i. TNF-alpha
 - j. IL-10
 - k. alpha and gamma-tocopherols
8. female subjects of child-bearing potential will have pregnancy test and the pregnancy test must be negative to participate in the study
9. a positive urine pregnancy test will be confirmed with a serum pregnancy test

Vitamin E for NASH Treatment in HIV Infected Individuals

10. transient elastography (FibroScan®) will be performed by a trained technician to measure steatosis by Controlled Attenuation Parameter (CAP) and fibrosis by liver stiffness (LSM)
11. MRI will be performed to measure hepatic fat content by PDFF according to the established protocol

Randomization

At the same visit, after the baseline evaluation is completed, subjects will be randomly assigned to either Group A: vitamin E in the form of all natural RRR-alpha tocopherol at 800 IU/d for 6 months (n = 28) or Group B: matching placebo for 6 months (n = 28). We will use a stratified randomization plan based on one factor, diabetes, similar to the recent FLINT trial (142). This will ensure two treatment groups having similar distribution of diabetes. A stratum specific computer-generated randomization list will be prepared by the study statistician to randomly assign study subjects in one of the two treatment groups. A block size of four will be used to ensure balance in number of subjects recruited in the two groups. Participants will be given sufficient drug for daily dosing and will be given detailed instructions about how to take the medicine.

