The primary outcome is the improvement in liver fat as assessed by MR-PDFF at end of treatment compared to baseline. To our knowledge, there are no data on studying the effect of vitamin E on MR-PDFF in NASH patients with HIV. Using an alpha of 5% and a two-sample independent t-test and equal variance assumption, a sample size of 25 per group will have 91% power to detect an effect size of 0.97 and will have 80% power to detect an effect size as small as 0.81. To ensure this number is achieved, 28 subjects per group will be recruited, allowing for 10% drop-out during the trial. The primary purpose of this pilot study is to generate preliminary data to estimate the mean and variability of improvement in liver fat with vitamin E in HIV infected patients with NASH.

Primary outcomes analysis: The primary analysis will be based on an analysis of covariance (ANCOVA) to compare the improvement in liver fat due to vitamin E relative to placebo. The model will include one dummy variable for treatment group indicator as well as baseline demographic characteristics and baseline liver fat. The 95% confidence intervals for the difference between the two treatment groups will be reported.

Vitamin E for NASH Treatment in HIV Infected Individuals

Secondary outcomes analysis: Secondary efficacy end points are continuous and as such the ANCOVA model will be used as described for analyzing the primary outcome except that the model will include the baseline value of the response variable.

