All endpoints are measured as the change from baseline to 24 weeks. The primary outcome measure is the change in hepatic fat content as measured by central reading of MR-PDFF performed at baseline and end of study. Secondary endpoints will be changes in inflammatory markers (liver enzymes, TNF-alpha, IL-10 levels), serum K-18, Liver stiffness and CAP measurement by TE, and MDA level as a marker of oxidative stress.

The primary outcome is the improvement in liver fat as assessed by MR-PDFF at end of treatment compared to baseline. To our knowledge, there are no data on studying the effect of vitamin E on MR-PDFF in NASH patients with HIV. Using an alpha of 5% and a two-sample independent t-test and equal variance assumption, a sample size of 25 per group will have 91% power to detect an effect size of 0.97 and will have 80% power to detect an effect size as small as 0.81. To ensure this number is achieved, 28 subjects per group will be recruited, allowing for 10% drop-out during the trial. The primary purpose of this pilot study is to generate preliminary data to estimate the mean and variability of improvement in liver fat with vitamin E in HIV infected patients with NASH.

Primary outcomes analysis: The primary analysis will be based on an analysis of covariance (ANCOVA) to compare the improvement in liver fat due to vitamin E relative to placebo. The model will include one dummy variable for treatment group indicator as well as baseline demographic characteristics and baseline liver fat. The 95% confidence intervals for the difference between the two treatment groups will be reported.

Secondary outcomes analysis: Secondary efficacy end points are continuous and as such the ANCOVA model will be used as described for analyzing the primary outcome except that the model will include the baseline value of the response variable.

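### The ANCOVA omits both site and diabetes, although the trial runs at two sites and randomises within diabetes strata; adding both terms is cheap and protects precision

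*Protocol*

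**What the plan says.** - **Sites.** Protocol section 2.0 sets the total at 56, "with approximately 28 individuals included at IU and 28 at Massachusetts General Hospital".
- **Randomisation.** Protocol section 4.0 states: "We will use a stratified randomization plan based on one factor, diabetes, similar to the recent FLINT trial (142"). It continues: "A stratum specific computer-generated randomization list will be prepared by the study statistician", and "A block size of four will be used to ensure balance in number of subjects recruited in the two groups". Allocation is 1:1 with 28 per arm. Site is not named as a stratum.
- **Model.** The SAP, under the primary outcomes analysis, states: "The model will include one dummy variable for treatment group indicator as well as baseline demographic characteristics and baseline liver fat". Protocol section 8.0 has the same sentence. The secondary endpoints use the same model with their own baseline value. The demographic characteristics are not listed. Section 4.0 collects age, sex, race and ethnicity, and site is not ordinarily counted as a demographic characteristic.
- **What bears on site differences.** MR-PDFF is read centrally (Protocol sections 7.0 and 8.0; SAP), and section 7.0 gives observer variability as the reason. MRI follows an established protocol at both time points. No central reading is described for elastography (liver stiffness and CAP). Neither document has a site term, a summary by site or a site sensitivity analysis.

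**The concern.** Two variables known for every patient at randomisation, site and the stratification factor, are missing from the model.

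Blocks within diabetes strata keep diabetes close to balanced between arms. If diabetes predicts change in liver fat, leaving it out keeps its variance in the error term and makes the interval wider than the design warrants.

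Site has no such balancing. If the sites differ in how much liver fat changes, through patient mix, delivery of lifestyle advice or image acquisition, two things follow. The residual variance rises, and a chance imbalance of arms within site moves the treatment estimate. The first matters particularly here because Protocol section 8.0 gives estimation of the mean and variability of improvement as the pilot's main purpose. An inflated SD would carry into the sample size of any later trial. Elastography is more exposed than MR-PDFF because no central reading is described for it.

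**Working it through.** **Inputs.** From the documents: two sites of about 28; 28 per arm; blocks of four within diabetes strata; 25 evaluable per arm; alpha 5%; effect sizes 0.97 and 0.81. Assumed: g, the site difference in mean change in within-site SD units, taken as 0.25, 0.5 and 1.0, because the documents give none.

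**1. The plan's own figures.** The noncentrality is d × √(n/2), with 48 degrees of freedom and a two-sided 5% test. The documents do not state sidedness, but two-sided reproduces their figures.
- d = 0.81: 0.81 × √12.5 = 2.86, power 80.1% (stated 80%).
- d = 0.97: 0.97 × √12.5 = 3.43, power 91.9% (stated 91%).
- 25 / 0.9 = 27.8, rounded up to 28 per arm.

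These figures are not in dispute.

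**2. Chance imbalance within site.** With 28:28 by arm and 28:28 by site, the number on vitamin E at one site is hypergeometric (56, 28, 28). Two-sided probabilities:
- 16:12 or worse: 42.3%
- 17:11 or worse: 18.1%
- 18:10 or worse: 6.0%

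Simulating blocks of four within two diabetes strata, with interleaved recruitment and 17 or 28 diabetic patients (assumed), gave 18.5% to 19.3% for 17:11 or worse and 6.2% to 6.6% for 18:10 or worse. If one site recruited entirely before the other, no simulated split exceeded 16:12, so these probabilities depend on interleaving.

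**3. Shift in the estimate.** At 17:11 the arms differ in site share by 17/28 − 11/28 = 0.214. Without a site term the contrast moves by 0.214 × g.

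**4. Error variance.** Two equal sites whose means differ by g add (g/2)² to a within-site variance of 1, so v = 1 + g²/4. Power without site uses d/√v on 48 degrees of freedom.

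| g | Residual SD, √v | Power at 0.81 | Power at 0.97 | Shift at 17:11 |
|---|---|---|---|---|
| 0 | 1.000 | 80.1% | 91.9% | 0 |
| 0.25 | 1.008 | 79.5% | 91.5% | 0.05 SD |
| 0.5 | 1.031 | 77.7% | 90.3% | 0.11 SD |
| 1.0 | 1.118 | 70.9% | 85.2% | 0.21 SD |

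With site in the model and arms balanced within site, power stays at 80.1% and 91.9% for every g. If the planning SD already contains site variance, the stated power holds and a site term adds to it: 82.1% at d = 0.81 if site explains 5% of the variance (g about 0.46), and 84.0% if 10% (g about 0.67).

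**5. Cost of the terms if they explain nothing.** At d = 0.81, power is 80.13% on 48 degrees of freedom, 80.09% on 47 (site) and 80.05% on 46 (site and diabetes). A further cost arises when site is correlated with arm by chance: at 17:11 the site term multiplies the variance of the treatment estimate by 1/(1 − 0.214²) = 1.048. Simulation with 50 evaluable patients and 4,000 runs, which includes this effect, gave power at 0.81 as follows.

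| g | Without site | With site |
|---|---|---|
| 0 | 80.5% | 79.6% |
| 0.5 | 77.2% | 79.2% |
| 1.0 | 70.3% | 79.3% |

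**6. Type I error.** In the same simulations it ran from 4.8% to 6.1%, with no material difference between the models with and without site.

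The effect of omitting diabetes was not sized. The documents give neither its prevalence nor its relation to change in liver fat.

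**The case against.** The strongest reply is that the plan already removes much of what site could do. The endpoint is a within-patient change, images are centrally read under an established protocol, baseline liver fat is a covariate, and lifestyle advice is described as standard. A stable scanner or patient-mix offset largely cancels. No passage says that scanners, operators or patients differ between sites. All of this stands, and it means g may be small. At 0.25 SD the power loss is 0.6 points, and in practice the site term may roughly break even. The shift is also modest against its standard error of √(2/25) = 0.28 SD: 0.11 SD is under 0.4 standard errors. What survives is a site difference in change itself, which neither central reading nor baseline adjustment removes.

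A reader might infer that omitting site biases the trial or confounds treatment with site. The documents do not support that. Allocation is random, any within-site imbalance is due to chance, and simulated type I error is no worse without the term.

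A reader might also infer that randomisation had to be stratified by site. That does not follow either. The protocol gives its reason for the single factor, similar diabetes distribution in the two arms, and one factor is a defensible choice in a 56-patient pilot.

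**Conclusion.** The point holds as an inexpensive improvement to the model, not as a flaw in validity. Both documents leave out site and the factor used to stratify randomisation. The consequence is lost precision and some sensitivity to chance imbalance. For site differences in change of 0.25 to 1.0 SD, power at effect size 0.81 falls by 0.6 to 9.2 points (80.1% to between 79.5% and 70.9%), the residual SD is inflated by 0.8% to 11.8%, and a 17:11 split moves the contrast by 0.05 to 0.21 SD.

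These sizes rest on the assumed range for g, on effect sizes expressed in within-site SD units, on interleaved recruitment, and on the plan's t-test framework rather than the full ANCOVA, whose demographic covariates are not listed. If the true site difference in change is at or below about 0.25 SD, the choice makes little difference either way.

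**What to change.** Before unblinding, amend the model statement in Protocol section 8.0 and in the SAP so that the primary and secondary ANCOVA include treatment, site, diabetes at randomisation, the baseline value of the response, and a named list of demographic covariates. Site and diabetes enter as fixed effects. The variability reported for planning later trials should be the residual SD from this model.

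The cost is two degrees of freedom and no new data. If neither factor matters, the lost degrees of freedom cost under 0.1 point of power. Allowing for chance arm-by-site imbalance, the simulated loss from the site term was about one point (80.5% to 79.6%).

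Optionally, and only if randomisation has not begun, prepare the blocks of four by site and diabetes. In simulation with an assumed 30% diabetic this held each site within 16:12. It needs two more lists and raises the SD of the overall arm-size imbalance from about 1.3 to 1.8 patients. If randomisation has begun, change only the model.
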